6. STUDY DRUG

6.1 Study Drug Administration

Ixazomib will be administered at 4mg oral dose once weekly on days 1, 8, and 15 of a 28-day cycle. Up to 6 total cycles of therapy will be delivered on trial, and patients will be followed through 1 year of total clinical follow up for study endpoints.

Patients experiencing a CR, PR, or stable disease at 6 months will be given the option to continue on ixazomib for up to an additional 6 cycles (for a total of up to 12 cycles, or maximum 36 doses). See section 4.3 for additional details.

Sufficient study drug will be dispensed at each study visit to cover one 28 day treatment cycle. Study patients will document their compliance through medication logs.

Ixazomib Administration

All protocol-specific criteria for administration of study drug must be met and documented before drug administration. Study drug will be administered or dispensed only to eligible

patients under the supervision of the investigator or identified subinvestigator(s). Patients should be monitored for toxicity, as necessary, and doses of Ixazomib should be modified as needed to accommodate patient tolerance to treatment; this may include symptomatic treatment, dose interruptions, and adjustments of Ixazomib dose (see Section 6.2). Due to the common side effect of nausea, it is recommended (but not required) that participants take Zofran (ondansetron) 8 mg PO, 30-60 minutes prior to each dose, and 8 hours after each dose. Additional doses of Zofran may be taken as needed, up to 24 mg in a 24-hour period.

The prescribed administration of Ixazomib doses in this study is 4mg oral dose once weekly on days 1, 8, and 15 of a 28-day cycle. Patients should be instructed to swallow Ixazomib capsules whole, with water, and not to break, chew, or open the capsules. Study drug should be taken on an empty stomach. Patients should not have any food or drink (other than water) for at least 2 hours before taking drug, and for at least 1 hour after taking drug. A total of approximately 8 ounces (240 mL) of water should be taken with the capsule.

Missed doses can be taken as soon as the patient remembers if the next scheduled dose is 72 hours or more away. A double dose should not be taken to make up for a missed dose. If the patient vomits after taking a dose, the patient should not repeat the dose but should resume dosing at the time of the next scheduled dose.

Ixazomib Destruction

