7.1.2 STUDY STOPPING RULES

While Ixazomib has demonstrated safety, it has not been previously studied in chronic GVHD therapy after allogeneic hematopoietic cell transplantation. Current evidence suggests that mortality after initiation of chronic GVHD therapy may be as high as 20% at 56 days in some high-risk patient groups (Blood and Marrow Transplant Clinical Trial Network Protocol 0801). In our current trial, we will implement a stopping rule based on a threshold rate of 10% treatment-related mortality occurring within 56 days (2 cycles) of starting treatment. If reasonable evidence exists that the rate on this trial exceeds this

threshold, then enrollment to the trial will be halted while data are reviewed. Reasonable evidence will be taken to mean that the lower bound of an exact 1-sided 80% confidence interval for the true non-relapse mortality rate exceeds 10%. The data will be evaluated at least every 10 patients, and will be triggered if 3 or more of 10, 4 or more of 20, 5 or more of 30, or 7 or more of 40 patients experience non-relapse mortality within the first 56 days.

Further details of the stopping rule include the following:

- (a) Treatment-related mortality is any death occurring while receiving study drug, or within 30 days after discontinuation of study drug, that is possibly, probably or definitely related to the drug
- (b) Relapse or progressive disease will factor into the attribution of cause, but will not automatically prevent a death from being classified as treatment-related
- (c) For purposes of this stopping rule, the count of patients (10, 20, etc) will reflect the order in which patients start treatment
- (d) If a DSMB review is required because the stopping rule is triggered, patients who are already enrolled and taking ixazomib may continue treatment, pending the outcome of that review. Any enrolled patient who has consented but not started study drug may not start ixazomib treatment, pending the outcome of that review.

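### The stopping rule's 30-day limit after discontinuation can leave drug-related deaths by day 56 out of the trigger count when ixazomib is stopped before day 26

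*Combined protocol and SAP*

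**What the plan says.** Section 7.1.2 runs on two clocks. The rule statement sets "a threshold rate of 10% treatment-related mortality occurring within 56 days (2 cycles) of starting treatment", so its window starts at the first dose. Detail (a) then defines treatment-related mortality as "any death occurring while receiving study drug, or within 30 days after discontinuation of study drug". It adds an attribution condition, namely a death "that is possibly, probably or definitely related to the drug". That window closes on a date that depends on when ixazomib is stopped.

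The section also names a second event. Its evidence criterion is that the "lower bound of an exact 1-sided 80% confidence interval for the true non-relapse mortality rate exceeds 10" per cent. Review is "triggered if 3 or more of 10, 4 or more of 20, 5 or more of 30, or 7 or more of 40 patients" have an event, and the same sentence says what the event is: "patients experience non-relapse mortality within the first 56 days". Neither sentence has a 30-day limit or an attribution test.

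Other relevant text:
- Section 6.1 schedules ixazomib as a "4mg oral dose once weekly on days 1, 8, and 15 of a 28-day cycle".
- Section 6.2.1 allows a dosing delay of up to 3 weeks, or at the discretion of the principal investigator, before treatment is discontinued.
- Section 6.11 keeps a patient who stops for toxicity in follow-up until treatment failure, which includes death.
- Section 8.2 collects adverse events to 30 days after the last dose, and later ones if a causal link is reasonably possible.
- Section 7.1.2 also sends every death through 6 months to the DSMB, outside the trigger.

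**The concern.** A rule with a 56-day window should count a drug-related death on day 50 regardless of when the drug was stopped. Under detail (a), such a death in a patient who stopped after the Day 8 dose is outside the count. Patients who stop in cycle 1 for toxicity are a group that an early safety rule should capture.

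The trigger limits are small, so one uncounted death can decide a look. The published operating characteristics are stated against a true event rate and make no allowance for qualifying deaths that the definition leaves out.

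**Working it through.** **Inputs.** Limits 3/10, 4/20, 5/30 and 7/40, the 80% bound against 10%, and the 56-day and 30-day windows (Section 7.1.2); 50 patients (Section 4.2); dosing days 1, 8 and 15 (Section 6.1).

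**Step 1: the limits.** The exact one-sided 80% lower bound for r events in n patients is the 0.20 quantile of Beta(r, n − r + 1).

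| Look | Bound at the limit | Bound with one event fewer |
|---|---|---|
| 3/10 | 15.8% | 8.3% |
| 4/20 | 11.7% | 7.8% |
| 5/30 | 10.5% | 7.8% |
| 7/40 | 12.0% | 9.9% |

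The limits reproduce. One event fewer falls below 10% at every look.

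**Step 2: the plan's operating characteristics.** I used an exact binomial recursion: carry forward the probability of k events without an earlier trigger, and stop at a look if k reaches the limit. The four listed looks alone give 23.5%, 56.3%, 82.0% and 94.5% at true rates 0.10, 0.15, 0.20 and 0.25. The plan states 25%, 62%, 87% and 97%. Adding a look at 50 patients with limit 8, which the same 80% criterion implies (bound 11.3%; 9.6% for 7/50), gives 25.6%, 62.3%, 87.6% and 97.3%, with average N 43.2, 33.5, 24.7 and 18.8 against the stated 43, 34, 25 and 19. That reproduces the table, so the five-look version is the baseline below. The 0.05 row reads 35 in the text available; the computed value is 3.1%.

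**Step 3: the gap.** Detail (a) counts to stop day + 30. Uncounted days = 56 − (stop day + 30), if positive.

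| Stop dated | Counted to day | Uncounted days |
|---|---|---|
| Day 1 | 31 | 25 |
| Day 8 | 38 | 18 |
| Day 15 | 45 | 11 |
| Day 25 | 55 | 1 |
| Day 26 | 56 | 0 |
| Day 29 | 59 | 0 |

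The first three rows assume that discontinuation is dated from the last dose.

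**Step 4: effect on the trigger.** Let f be the share of qualifying 56-day deaths that fall in the gap. The documents give no value, so f is an assumption, shown from 0 to 20%. The counted rate is p(1 − f); for example, 0.15 × 0.90 = 0.135 and 0.20 × 0.80 = 0.16.

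| f | P(stop), p = 0.15 | P(stop), p = 0.20 |
|---|---|---|
| 0 | 62.3% | 87.6% |
| 5% | 57.0% | 84.0% |
| 10% | 51.5% | 79.6% |
| 20% | 40.2% | 68.7% |

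**Step 5: how large could f be?** If deaths were spread evenly from last dose to day 56 (an assumption), the gap would hold 25/55 = 45.5% of deaths after a Day 1 stop, 18/48 = 37.5% after Day 8 and 11/41 = 26.8% after Day 15. An overall f of 5% would then need 0.05/0.268 = 19% of all qualifying deaths to be in Day 15 stoppers. An f of 20% would need 0.20/0.268 = 75%, or 0.20/0.455 = 44% if all had stopped on Day 1. The upper end of the range is therefore demanding.

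**The case against.** The strongest reply is that the numerical trigger already counts these deaths: it uses non-relapse mortality to day 56 with no 30-day limit. Under that wording a non-relapse death in the gap counts. This stands, but it does not settle the matter. The rule statement, detail (a) and the attribution language in detail (b) all use treatment-related mortality, so someone applying the rule could reasonably follow detail (a). If treatment-related mortality were chosen as the single event and detail (a) left alone, the gap would remain.

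Second, discontinuation is not defined as the last dose. Section 8.2 refers to the last dose when that is meant, and Section 6.2.1 allows a delay before treatment is discontinued. A patient last dosed on Day 15 and recorded as discontinued on day 26 or later has no gap. This also stands: 25, 18 and 11 days hold only when the stop is dated from the last dose. It equally means that the safety count depends on how a stop is dated.

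Third, a 30-day attribution window may be deliberate, and the DSMB receives all deaths through 6 months. That limits the harm, but the automatic halt to enrollment depends on the count, and discussion of other deaths is left to the DSMB as needed.

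Two stronger readings are not supported. A reader might infer that every patient who stops in cycle 1 and dies before day 56 is dropped; detail (a) counts related deaths within 30 days of stopping, and a stop on day 26 or later loses nothing. A reader might also infer a drastic loss, for example with one quarter of deaths in the gap. Under the even spread in step 5, that needs 55% (0.25/0.455) to 93% (0.25/0.268) of qualifying deaths to be in patients who stopped after a single given cycle 1 dose, and nothing in the documents suggests this.

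**Conclusion.** The concern holds in limited form. If detail (a) governs, drug-related deaths later than stop day + 30 and no later than day 56 are missing from the trigger count, and this requires a stop dated before day 26. If the trigger sentence governs, non-relapse deaths in that interval are counted. Section 7.1.2 supports both readings and must be reconciled.

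The loss cannot be sized from the documents. It is zero if no qualifying death falls in the gap. For an assumed share of 5% to 20%, the chance of a trigger falls by about 5 to 22 percentage points at a true rate of 15%, and by about 4 to 19 points at 20%. These figures rest on the five-look rule, including the unlisted look at 50 patients. They do not show that unsafe outcomes would go unseen by the DSMB.

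**What to change.** In Section 7.1.2:
- State that, for this stopping rule, every qualifying death within 56 days of the first dose counts, whatever the date ixazomib was discontinued.
- Keep the 30-day limit for adverse-event reporting only.
- Use one event name in the rule statement, the confidence bound, the trigger sentence and detail (a). The choice between treatment-related and non-relapse mortality is for the sponsor; the window wording is needed in either case.

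The cost is a short text amendment. No new data are needed, because follow-up continues after a toxicity stop (Section 6.11), possibly related late events are recorded (Section 8.2) and deaths through 6 months are already reported. Once every qualifying death to day 56 is counted, the f = 0 row applies, which matches the published operating characteristics.

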8. ADVERSE EVENTS

8.1 Definitions

- **Pretreatment Event Definition**

A pretreatment event is any untoward medical occurrence in a patient or subject who has signed informed consent to participate in a study but before administration of any study medication; it does not necessarily have to have a causal relationship with study participation.

- **Adverse Event**

An adverse event is any untoward medical occurrence associated with the use of a drug in humans, whether or not considered drug related. It can be any unfavorable and unintended sign (e.g., an abnormal laboratory finding), symptom, or disease, temporally associated with the use of a drug whether or not it is related to the drug. This includes any newly occurring event, or a previous condition that has increased in severity or frequency since the administration of study drug.

An abnormal laboratory value will not be assessed as an AE unless that value leads to discontinuation or delay in treatment, dose modification, therapeutic intervention, or is considered by the investigator to be a clinically significant change from baseline.

AE Grading Criteria:

The study site will grade the severity of adverse events experienced by study participants on a scale from 1 to 5 according to NCI CTCAE v4.0 or current version. Grade 1 and grade 2

adverse events do not require reporting. Adverse events not included in the NCI CTCAE should be recorded and graded according to the General Grade Definition provided below:

ADVERSE EVENT GENERAL GRADE DEFINITIONS

Grade 1	Mild	Asymptomatic or mild symptoms; clinical or diagnostic observations only; intervention not indicated
Grade 2	Moderate	Minimal, local or non-invasive intervention indicated; limiting age-appropriate instrumental ADL*
Grade 3	Severe	Severe or medically significant, but not immediately life-threatening; hospitalization or prolongation of hospitalization indicated; disabling; limiting self-care ADL **
Grade 4	Life-threatening	Life-threatening consequences; urgent intervention indicated
Grade 5	Death related to AE	Death related to AE

*Instrumental ADL: Preparing meals, shopping for groceries or clothes, using the telephone, managing money, etc.

**Self-care ADL: Bathing, dressing and undressing, feeding self, using the toilet, taking medications, and not bedridden.

○Suspected Adverse Reactions – a subset of Adverse Events based on causality

A suspected adverse reaction is any adverse event for which there is a *reasonable possibility* that the drug caused the event. *Reasonable possibility* means there is evidence to suggest a causal relationship between the drug and the event. Some examples are:

- A single occurrence of an event that is uncommon and known to be strongly associated with drug exposure.
- One or more occurrences of an event that is not commonly associated with drug exposure, but is otherwise uncommon in the population exposed to the drug. If the event occurs in association with other factors strongly suggesting causation (e.g., strong temporal association, event recurs on re-challenge), a single case may be sufficiently persuasive. Often, more than one occurrence is needed before the sponsor-investigator can determine that there is a reasonable possibility that the drug caused the event.

- An aggregate analysis of events observed in a clinical trial that indicates those events occur more frequently in the drug treatment group than in a similar population not receiving the study drug.

If there is reason to conclude with certainty that the drug caused the event, the event is classified as an **Adverse Reaction**.

- o **Unexpected**

An adverse event is considered unexpected *if it is not listed in the investigator brochure, or is not listed at the specificity or severity that has been observed in the event.* “Unexpected” also refers to adverse events that are mentioned in the investigator brochure as occurring with a class of drugs or as anticipated from the pharmacological properties of the drug, but are not specifically mentioned as occurring with the particular drug under investigation.

- o **Serious**

An adverse event is considered “serious” if, in the view of either the investigator or the sponsor, it results in any of the following outcomes:

1. Death
2. A life-threatening adverse event (places the subject at an immediate risk of death)
3. Inpatient hospitalization or prolongation of existing hospitalization
4. A persistent or significant disability or incapacitation
5. A congenital anomaly or birth defect
6. Is a **medically important event**. This refers to an AE that may not result in death, be immediately life threatening, or require hospitalization, but may be considered serious when, based on appropriate medical judgment, may jeopardize the patient, require medical or surgical intervention to prevent 1 of the outcomes listed above, or involves suspected transmission via a medicinal product of an infectious agent. Examples of such medical events include allergic bronchospasm requiring intensive treatment in an emergency room or at home, blood dyscrasias or convulsions that do not result in inpatient hospitalization, or the development of drug dependency or drug abuse; any organism, virus, or infectious particle (eg, prion protein transmitting Transmissible Spongiform Encephalopathy), pathogenic or nonpathogenic, is considered an infectious agent.

Clarification should be made between a serious AE (SAE) and an AE that is considered severe in intensity (Grade 3 or 4), because the terms serious and severe are NOT

synonymous. The general term *severe* is often used to describe the intensity (severity) of a specific event; the event itself, however, may be of relatively minor medical significance (such as a Grade 3 headache). This is NOT the same as *serious*, which is based on patient/event outcome or action criteria described above, and is usually associated with events that pose a threat to a patient's life or ability to function. A severe AE (Grade 3 or 4) does not necessarily need to be considered serious. For example, a white blood cell count of 1000/mm³ to less than 2000 is considered Grade 3 (severe) but may not be considered serious. Seriousness (not intensity) serves as a guide for defining regulatory reporting obligations.

8.2 Recording of Adverse Events

The study will collect all Grade 3 and above adverse events (*except* abnormal labs as outlined in section 8.1, and the exceptions listed below), regardless of relationship to study therapy or study procedures. Severity grading will be based on the current version of the Common Terminology Criteria for Adverse Events (CTCAE). Grade 1 and 2 events will not be collected.

Adverse events will be collected from the time the patient signs the informed consent until 30 days after the last dose of Ixazomib. Events that occur after this time will be recorded only if there is a reasonable possibility that the event was caused by a study procedure or Ixazomib. All recordable adverse events will be followed until resolution.

Reporting procedures:

- All non-serious, Grade 3 and above adverse events must be recorded in the database within 20 days of becoming aware of the event.
- Exceptions:

The following are frequent events in the chronic GVHD population and will not be recorded as adverse events *as long as they are not serious*:

- Abnormalities present at study enrollment: Will not be considered adverse events, unless such abnormalities worsen (i.e. increase in frequency, intensity, or present new complications or untoward events) during study follow up
- Electrolyte abnormalities: Increase or decrease in sodium, potassium, chloride, bicarbonate, phosphorus, magnesium, calcium, hyperglycemia following steroid

therapy

- **Ocular:** GVHD related eye dryness, discomfort, requirement for moisturizing eye drops or other topical GVHD ocular therapies or interventions (e.g. punctal plugs, scleral lenses), changes in visual acuity.
- **Dermatology:** Nail changes, GVHD rash (to include erythema, scleroderma, ulceration, lichenoid changes, hyper- or hypo-pigmentation, dry skin and alopecia) or cushingoid appearance due to steroid therapy.
- **Gastrointestinal:** Xerostomia, oral ulcers or other GVHD associated lesions, oral pain or sensitivity, anorexia, difficulty swallowing due to esophageal stricture or narrowing, nausea/vomiting, salivary gland changes, GVHD associated abdominal pain, bloating, diarrhea, weight loss
- **Respiratory:** shortness of breath, cough, or oxygen requirement associated with pulmonary chronic GVHD involvement
- **Growth and Development:** Reduced growth velocity, delayed puberty.
- **Musculoskeletal changes:** Avascular necrosis, fracture, arthritis, osteoporosis, decrease in range of motion associated with joint or fascial GVHD involvement
- **Sexual Function:** Erectile dysfunction, infertility, amenorrhea, vaginal stenosis, vaginal dryness or discomfort.
- **Events secondary to routine procedures performed for chronic GVHD therapies:** Extracorporeal photopheresis, PUVA therapy.

Non-serious adverse events collected in the database will be compiled by the coordinating center and reported to the DSMB approximately every 6 months.

All **serious adverse events** must be reported in the database within 24 hours of becoming aware of the event. Significant and relevant follow-up information should also be reported as soon as possible.

- **Exception:**
 - Hospitalization for elective treatment of a pre-existing condition that did not worsen from baseline is not considered an SAE.

The database will notify the coordinating center and sponsor-investigator when a serious adverse event has been entered. The sponsor-investigator will then determine whether the event meets the criteria for expedited reporting (see below) and will work with the coordinating center to prepare the IND Safety Report.

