A summary of the safety profile of patients treated in Study C16004 is outlined in Table 1-4. Overall, 92% of patients experienced a TEAE of any grade and of any cause. Peripheral neuropathy was limited to Grade 1/2 in 6 patients, with 3 patients reporting baseline Grade 1 PN at study entry.

Table 1-4 Study C16004, Oral Ixazomib, Single Agent, Given Weekly: Most Common TEAEs as of 30 April 12 (N= 52)

Most Common (> 20%) Any Grade and Irrespective of Cause	Thrombocytopenia (54%) Fatigue (48%) Nausea (44%), diarrhea (44%) Vomiting (37%) Decreased appetite (33%) Rash* (31%) Anemia (25%) Neutropenia (23%)
Drug-Related Grade ≥ 3 in > 5% of patients	Thrombocytopenia (38%) Diarrhea and neutropenia 17% (each), fatigue and lymphopenia 10% (each), nausea and decreased appetite 8% (each) and vomiting 6%

Source: Ixazomib Investigator's Brochure Edition 6

* Rash includes preferred terms of rash macular, rash, maculo-papular, rash morbilliform, rash pruritic,

pruritus,, rash erythematous, exfoliative rash, and rash popular

Dose reductions required were due to AEs that included rash, neutropenia, thrombocytopenia, diarrhea, nausea, vomiting, dehydration, hypotension, increase in serum creatinine, abdominal pain, ileus, fatigue, and pneumonia. The AEs reported for the 5 patients who were required to discontinue treatment included Grade 2 Ixazomib-related nausea/vomiting in 1 patient treated above the MTD, Grade 3 Ixazomib-related diarrhea in a second patient, related Grade 3 thrombocytopenia, related Grade 2 dyspnea, and notrelated Grade 4 elevation in creatinine(1 patient each). There were no on-study deaths.

Study C16007 is evaluating single agent weekly , Day 1, 8, and 15 of a 28-day cycle, oral dosing in patients with RRAL after at least 1 prior therapy. The objectives of this study are to determine the safety, tolerability, and MTD, as well as to determine hematologic and organ response rates in this patient population. The starting dose level was selected from Study C16004 as previously described. In Study C16007 the dose was switched from the BSA-based dosing to the fixed dose, thereby the 4.0 mg fixed starting dose in Study C16007 corresponds to the 2.23 mg/m² dose (one dose level below MTD) from Study C16004. This study is currently enrolling patients in the dose-expansion portion of the trial.

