
 • ANC $< 1.0 \times 10^9/L$, platelet count $< 75 \times 10^9/L$, or other non-hematologic toxicities $>$ Grade 1 or not to the patient's baseline condition 	
 • Hold Ixazomib until resolution as per criteria Section 6.2. • Upon recovery, reduce Ixazomib 1 dose level. • The maximum delay before treatment should be discontinued will be 3 weeks or at the discretion of the PI.
Dose Modifications for Subsequent Treatment Cycles	

 • All hematologic toxicities 	
 • For hematologic toxicity that occurs during a cycle but recover in time for the start of the next cycle: 
 ◦ If dose was reduced within the cycle, start the next cycle at that same dose. ◦ If due to toxicity timing, ie, after Day 15 dosing thus a dose reduction was not required at that point in the cycle, reduce Ixazomib by 1 dose level at the start of that cycle. ◦ Do not reduce the dose both within a cycle and at the start of the cycle for the same most severe toxicity.

Table 6-3 Ixazomib Treatment Modification (Delays, Reductions, and Discontinuations) Due to Adverse Events (Non-Hematologic Toxicities)

Adverse Event (Severity)	Action on Study Drug	Further Considerations
Peripheral Neuropathy:		
Grade 1 peripheral neuropathy	
 • No action 	Grade 1 signs and symptoms: asymptomatic; without pain or loss of function; clinical or diagnostic observations only [14]
New or worsening Grade 1 peripheral neuropathy with pain or Grade 2	
 • Hold study drug until resolution to Grade ≤ 1 or baseline • Resume at same dose level 	Grade 2 signs and symptoms: Moderate symptoms; limiting instrumental activities of daily living (ADL) [14]
New or worsening Grade 2 peripheral neuropathy with pain or Grade 3	
 • Hold study drug until resolution to Grade ≤ 1 or baseline • Reduce study drug to next lower dose upon recovery 	Grade 3 signs and symptoms: severe symptoms; limiting self-care ADL; assistive device indicated [14]
New or worsening Grade 4 peripheral neuropathy	
 • Discontinue study drug 	
Grade 2 Rash	Symptomatic recommendations as per section 6.6	The investigator and project clinician may discuss considerations for dose modifications and symptom management.

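### Non-serious Grade 1-2 events that delay, hold, reduce or stop ixazomib are not collected, so dose changes can stand in the data with no adverse event behind them

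*Combined protocol and SAP*

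**What the plan says.** **Collection rules.** Section 8.2 sets the floor: "All non-serious, Grade 3 and above adverse events must be recorded in the database within 20 days of becoming aware of the event". It adds that "Grade 1 and 2 events will not be collected". Section 8.1 says the same of Grade 1 and 2, that such "adverse events do not require reporting". Serious events have no grade floor; they "must be reported in the database within 24 hours of becoming aware of the event". A change to dosing is not among the seriousness criteria in Section 8.1. Section 8.2 also lists events common in chronic GVHD, nausea and vomiting among them, that are not recorded at any grade unless serious.

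**Dosing rules.** Table 6-3 takes no action for plain Grade 1 neuropathy. It holds the drug for "New or worsening Grade 1 peripheral neuropathy with pain or Grade 2", and holds and then reduces it for "New or worsening Grade 2 peripheral neuropathy with pain or Grade 3". Section 6.2.1 allows a new cycle only when non-hematologic toxicity, alopecia aside, is back to Grade 1 or lower or to baseline. It ends treatment after a 3-week delay unless the principal investigator decides otherwise. Table 6-2 reduces by one level after such a delay, and the note after Table 6-3 bars going back up. Section 6.11 lists unresolved toxicity as a reason to stop, with no grade given.

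**The concern.** The two sets of rules do not meet. A non-serious Grade 2 event can delay a cycle, lower the dose for the rest of the study or contribute to stopping, and still fall below the collection floor. The data would then show a missed dose, a lower level or an early stop with no event to explain it.

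Section 8.1 makes the mismatch visible for laboratory values. It counts an abnormal value as an adverse event when it leads to delay, dose modification or discontinuation; the floor then drops that event if it is Grade 1 or 2.

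At stake is the account of why patients could not stay on the drug. Section 7.1.2 notes that ixazomib had not been studied in this setting. Section 5.2 admits patients with painless Grade 2 neuropathy, and Section 4.3 allows up to 12 cycles. The roughly six-monthly DSMB compilation (Section 8.2) and the IND Annual Report (Section 8.3) are built from collected events only.

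**Working it through.** **Step 1. Set the dosing rules against the floor (non-serious events).**

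| Rule | Trigger below Grade 3 | Action | Collected? |
|---|---|---|---|
| Table 6-3 | Plain Grade 1 neuropathy | None | No |
| Table 6-3 | Grade 1 neuropathy with pain, or Grade 2 | Hold, resume at same level | No |
| Table 6-3 | Grade 2 neuropathy with pain | Hold, then reduce | No |
| 6.2.1, Table 6-2 | Non-hematologic toxicity at Grade 2 and above baseline when a cycle is due | Delay, then reduce; stop after 3 weeks or at the investigator's discretion | No |
| 6.11 | Unresolved toxicity, grade not stated | Stop | Not if Grade 1-2 |
| 8.1 | Grade 1-2 laboratory value that changes dosing | As above | No |

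Only the first row involves no dosing action.

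**Step 2. Look for another place that records the cause.**
- Section 4.3: diaries track doses, not reasons.
- Section 6.10: records of drug receipt and dispensing.
- Section 6.11: an End of Treatment visit, with no instruction to record the reason for stopping.
- Section 6.12: a primary reason on the CRF, but for a patient's withdrawal from the study.
- Section 8.5: the investigator determines intensity and relationship for non-serious events, but nothing sends a Grade 1-2 event to the database.

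None requires the grade or cause of a dosing action to be held in the database.

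**Step 3. What the cited trials show, as context.**

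*C16004* (single agent, weekly, N = 52; Section 1.6): "Peripheral neuropathy was limited to Grade 1/2 in 6 patients". Three patients had Grade 1 neuropathy at entry. 6/52 = 11.5%, none at Grade 3.

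*C16005* (with lenalidomide and dexamethasone; Section 1.7): neuropathy in 13%, one patient at Grade 3. The figure sits with the 53 patients treated at the MTD, and 7/53 = 13.2% reproduces it. No whole count out of 65 does: 8/65 = 12.3%, 9/65 = 13.8%.

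Cases below Grade 3: (6 + 6)/(6 + 7) = 12/13 = 92%.

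This does not count dosing actions. The 12 cases are not divided by Grade 1 versus 2, by pain, or by action taken. If all were plain Grade 1, none would have triggered a hold under Table 6-3; if all were new or worsening and either painful or Grade 2, all 12 would have. The range is 0 to 12 of 13.

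*Discontinuations in C16004.* Five patients stopped for adverse events: two for Grade 2 events, two for Grade 3 and one for Grade 4. The Grade 2 events "included Grade 2 Ixazomib-related nausea/vomiting in 1 patient treated above the MTD" and one case of dyspnea. 2/5 = 40%. The exact 95% interval (Clopper-Pearson, with limits Beta(0.025; 2, 4) and Beta(0.975; 3, 3)) is 5% to 85%. Under this protocol's floor, neither would be recorded unless serious. The nausea/vomiting case would also be dropped by the Section 8.2 exempt list, whatever its grade.

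**The case against.** The strongest reply is that the floor is a deliberate choice, stated consistently in Sections 8.1 and 8.2 and reasonable in patients with so much background morbidity. The objectives and endpoints cover efficacy, survival, patient-reported and functional outcomes, and biology; none is a tolerability endpoint. Serious events are reported at any grade, and deaths have their own stopping rule. All of this stands, which is why the remedy keeps the floor.

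A second reply is that absence from the protocol does not prove absence from the data. The CRFs and the Manual of Operations named in Section 6.7 are not part of the document. Section 6.1 requires criteria for giving the drug to be met and documented, and schedule deviations need approval, so source records should exist. This also stands. What is missing is a stated requirement that the database hold the information.

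A reader might go further in three ways that the document does not support:
- *That ixazomib is held for all Grade 1-2 neuropathy.* Plain Grade 1 calls for no action, and Table 6-3 orders permanent stopping for neuropathy only at Grade 4. A lower grade can end treatment only through the delay limit or the unresolved-toxicity rule.
- *That 92% of dose-limiting neuropathy would be lost, or that the trial would report almost no neuropathy.* The 92% covers all neuropathy below Grade 3, whether or not dosing changed, and a table of Grade 3 and higher events makes no claim about lower grades.
- *That 40% of discontinuations would go unexplained.* That is 2 of 5, and one of the two patients was dosed above the MTD.

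**Conclusion.** The gap is real and worth closing. As written, a delay, hold, reduction or discontinuation caused by a non-serious Grade 1-2 event can enter the data without its cause, and the DSMB and IND compilations would understate toxicity that limits dosing. The primary endpoint and the mortality stopping rule are not affected.

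Its size cannot be computed from the document. The cited figures show only that low-grade neuropathy was the usual form and that Grade 2 events did end treatment in some patients. Carrying them over to this trial would be an assumption of unknown direction: C16005 was a combination trial, C16004 covered doses from 0.24 to 3.95 mg/m² with a median of 2 cycles, and this trial plans up to 6 or 12 cycles at a 4 mg starting dose.

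The conclusion assumes that no CRF or manual outside the document already requires the cause of each dosing action.

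**What to change.** Add to Section 8.2, and mirror in Section 8.1:

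*Exception: any Grade 1 or 2 event, including peripheral neuropathy or a laboratory abnormality, that leads to a delay, hold, dose reduction or discontinuation of ixazomib is recorded with grade, relationship and action taken; this exception overrides the list of exempt events below.*

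The last clause is needed because, without it, an event such as nausea or vomiting that stops the drug would still be dropped by the exempt list. All other Grade 1-2 events stay uncollected, and no dosing rule changes.

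The cost is a few extra adverse event entries, for events that sites must already grade to apply the dose-modification tables. If a CRF already captures the cause and grade of each dosing action, a cross-reference to it in Section 8.2 would do most of the work.
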